2.4.3 Best Overall Response: All Time Points

The best overall response is determined once all the data for the participant is known.

Table A-1 Time Point	Table A-1 Time Point Response: Participants with Target (+/- Non-target) Disease										
Target Lesions	Non-target Lesions	New Lesions	Overall Response								
CR	CR	No	CR								
CR	Non-CR/non-PD	No	PR								
CR	Not evaluated	No	PR								
PR	Non-PD or not all evaluated	No	PR								
SD	Non-PD or not all evaluated	No	SD								
Not all evaluated	Non-PD	No	NE								
PD	Any	Yes or No	PD								
Any	PD	Yes or No	PD								
Any	Any	Yes	PD								

Abbreviations: CR: complete response; PR: partial response; SD: stable disease; PD: progressive disease; NE: non evaluable.

Best response determination in trials where confirmation of complete or partial response IS required: Complete or partial responses may be claimed only if the objective response is confirmed on a follow-up scan obtained no less than 4 weeks after the initial scan demonstrating an objective response. In this circumstance, the BOR can be interpreted as in Table A-2.

ImmunoGen, Inc 29 March 2022

IMGC936 Clinical Study Protocol: IMGC936-0901 Amendment 3

Table A-2 Best Ov	erall Response when Confi	rmation of CR and PR Required
Overall Response First Time Point	Overall Response Subsequent Time Point	Best Overall Response
CR	CR	CR
CR	PR	SD, PD or PR ^a
CR	SD	SD
CR	PD	SD
CR	NE	SD
PR	CR	PR
PR	PR	PR
PR	SD	SD
PR	PD	SD provided minimum criteria for SD duration met, otherwise, PD
PR NE		SD provided minimum criteria for SD duration met, otherwise, NE
NE	NE	NE

Abbreviations: CR: complete response; PR: partial response; SD: stable disease; PD: progressive disease; NE: not evaluable.

Special Notes on Response Assessment

When nodal disease is included in the sum of target lesions and the nodes decrease to 'normal' size (< 10 mm), they may still have a measurement reported on scans This measurement should be recorded even though the nodes are normal in order not to overstate progression should it be based on increase in size of the nodes. As noted earlier, this means that participants with CR may not have a total sum of 'zero' on the eCRF.

Participants with a global deterioration of health status requiring discontinuation of study drug without objective evidence of disease progression at that time should be reported as 'symptomatic deterioration'. Every effort should be made to document objective progression even after discontinuation of study drug. Symptomatic deterioration is not a descriptor of an objective response: it is a reason for stopping study drug. The objective response status of such participants is to be determined by evaluation of target and non-target disease as shown in Table A-1 and Table A-2.

For equivocal findings of progression (eg, very small and uncertain new lesions; cystic changes or necrosis in existing lesions), study drug may continue until the next scheduled assessment. If at the next scheduled assessment, progression is confirmed, the date of progression should be the earlier date when progression was suspected.

^a If a CR is truly met at first time point, then any disease seen at a subsequent time point, even disease meeting PR criteria relative to baseline, makes the disease PD at that point (since disease must have reappeared after CR). Best response would depend on whether minimum duration for SD was met. However, sometimes 'CR' may be claimed when subsequent scans suggest small lesions were likely still present and in fact the participant had PR, not CR at the first time point. Under these circumstances, the original CR should be changed to PR and the best response is PR.

2.5 Confirmation/Duration of Response

2.5.1 Confirmation

Objective responses should be confirmed by CT and/or MRI scans obtained no less than 4 weeks after the original scan.

2.5.2 Duration of Overall Response

The duration of overall response is measured from the time measurement criteria are first met for CR/PR (whichever is first recorded) until the first date that recurrent or progressive disease is objectively documented (taking as reference for PD the smallest measurements recorded on study). The duration of overall complete response is measured from the time measurement criteria are first met for CR until the first date that recurrent disease is objectively documented.

2.5.3 Duration of Stable Disease

SD is measured from the start of study drug administration until criteria for progression are met, taking as reference the smallest sum on study (if the baseline sum is the smallest, this is the reference for calculation of PD).

APPENDIX 7. EXAMPLES OF CLINICAL SUBSTRATES FOR CYP3A-MEDIATED METABOLISM

CYP Enzyme	Clinical substrate
CYP3A Strong Inhibitor	boceprevir, cobicistat, danoprevir and ritonavir, elvitegravir and ritonavir, grapefruit juice, indinavir and ritonavir, itraconazole, ketoconazole, lopinavir and ritonavir, paritaprevir and ritonavir and (ombitasvir and/or dasabuvir), posaconazole, ritonavir, saquinavir and ritonavir, telaprevir tipranavir and ritonavir, telithromycin, troleandomycin, voriconazole
CYP3A Strong Inducer	apalutamide, carbamazepine, enzalutamide, mitotane, phenytoin, rifampin, St. John's wort

Source: FDA drug development resources (as of 29 July 2020)

APPENDIX 8. ECOG AND KARNOFSKY PERFORMANCE SCALES

ECOG Performance Scale

Grade	Description
0	Fully active, able to carry on all predisease performance without restriction.
1	Restricted in physically strenuous activity, but ambulatory and able to carry out work of a light or sedentary nature (eg, light house work or office work).
2	Ambulatory and capable of all self-care, but unable to carry out any work activities. Up and about more than 50% of waking hours.
3	Capable of only limited self-care, confined to bed or chair more than 50% of waking hours.
4	Completely disabled. Cannot carry-on any self-care. Totally confined to bed or chair.
5	Dead.

Karnofsky Performance Scale

Able to carry on normal activity and to work; no special care needed.	100	Normal no complaints; no evidence of disease.
	90	Able to carry on normal activity; minor signs or symptoms of disease.
	80	Normal activity with effort; some signs or symptoms of disease.
Unable to work; able to live at home and care for most personal needs; varying amount of assistance needed.	70	Cares for self; unable to carry on normal activity or to do active work.
	60	Requires occasional assistance but is able to care for most of his personal needs.
	50	Requires considerable assistance and frequent medical care.
Unable to care for self; requires equivalent of institutional or hospital care; disease may be progressing rapidly.	40	Disabled; requires special care and assistance.
	30	Severely disable; hospital admission is indicated, although death not imminent.
	20	Very sick; hospital admission necessary; active supportive treatment necessary.
	10	Moribund; fatal processes progressing rapidly.
	0	Dead.

# LIST OF ABBREVIATIONS

Abbreviation or Specialist Term	Explanation
AE	Adverse event
ALT	Alanine aminotransferase (SGPT)
AST	Aspartate aminotransferase (SGOT)
BP	Blood pressure
CR	Complete response
CRC	Cohort Review Committee
CRF	Case report form
CTCAE	Common Terminology Criteria for Adverse Events
DLT	Dose-limiting toxicity
DoR	Duration of response
ECG	Electrocardiogram
ЕСНО	Echocardiogram
ECOG	Eastern Cooperative Oncology Group
eCRF	Electronic case report form
IV	Intravenous(ly)
MedDRA	Medical Dictionary for Regulatory Activities
MTD	Maximum tolerated dose
MUGA	Multigated acquisition
ORR	Objective response rate
PD	Progressive disease
PK	Pharmacokinetics
PR	Partial response
PT	Preferred term
QTc	Corrected QT interval
RP2D	Recommended Phase 2 dose
SAE	Serious adverse event
SAP	Statistical analysis plan
SD	Stable disease
SOC	System organ classes
TEAE	Treatment-emergent adverse event
ULN	Upper limit of normal

#### 1. INTRODUCTION

## 1.1. Background

This document describes the statistical analysis plan (SAP) for the study IMGC936-0901, based on the Protocol Amendment #3, dated on 29-March-2022.

This SAP will govern the analysis of this study. Any deviations from the SAP will be documented as such in the study report.

#### 2. STUDY OBJECTIVES

#### 2.1. Dose Escalation Phase

## 2.1.1. Primary Objectives

• To assess safety, tolerability, and dose-limiting toxicities (DLTs), and determine a maximum tolerated dose (MTD), or maximum administered dose (MAD) (if no MTD is defined), and recommended Phase 2 dose (RP2D) for IMGC936 administered intravenously (IV)

## 2.1.2. Secondary Objectives

- To characterize pharmacokinetics (PK) and immunogenicity of IMGC936
- To describe objective response rate (ORR) and duration of response (DoR) for IMGC936 using Response Evaluation Criteria in Solid Tumors version 1.1 (RECIST 1.1)

# 2.1.3. Exploratory objectives

- To explore progression-free survival (PFS)
- To explore potential biomarkers of clinical and/or immunologic response to IMGC936 in blood and tumor tissue
- To explore the relationship between baseline ADAM9 (a disintegrin and metalloprotease domain-containing protein 9) expression and antitumor activity

#### 2.2. Dose Expansion Phase

- 2.2.1. Primary:
  - To describe ORR for IMGC936 using RECIST v1.1
- 2.2.2. Secondary:
  - To characterize safety and tolerability for IMGC936
  - To characterize PK and immunogenicity of IMGC936
  - To describe DoR and PFS
- 2.2.3. Exploratory:

- To explore potential biomarkers of clinical and/or immunologic response to IMGC936 in blood and tumor tissue
- To explore the relationship between baseline ADAM9 expression and antitumor activity
- To explore ocular primary prophylaxis regimens

#### 3. STUDY DESIGN

## 3.1. Overall Study Design and Plan

This study is a Phase 1/2, first-in-human, open-label, dose-escalation study designed to characterize the safety, tolerability, PK, pharmacodynamics, immunogenicity, and preliminary antitumor activity of IMGC936 administered by IV infusion. Participants with unresectable, relapsed or refractory, locally advanced or metastatic non-squamous NSCLC, TNBC, CRC, gastroesophageal cancer, or pancreatic cancer will be enrolled globally in approximately 26 sites. Up to a maximum of 345 participants will be enrolled in the study if all expansion cohorts are fully enrolled.

Each cycle is 21 days for Schedule A and 28 days for Schedule B. IMGC936 is administered via IV infusion at the assigned dose for each cohort. Infusion duration will vary depending on dose and participant tolerability. Participants may continue on study drug until disease progression, AE requiring discontinuation, withdrawal of consent, physician decision, or other discontinuation criteria are met.

Participants will be followed for safety throughout the study. Any participant who discontinues study drug should return to the study site for an end of treatment visit (EOTV). The visit should be performed within 30 days following last dose of study drug whenever possible.

#### 3.2. Dose escalation

The goal is to characterize safety and tolerability of IMGC936 to define the single-agent maximum tolerated dose (MTD) and select a recommended Phase 2 dose (RP2D). If no MTD is defined after escalation to the maximum protocol-specified dose, then the highest dose level administered will be designated as the maximum administered dose (MAD).

Up to 72 evaluable participants will be enrolled in the Dose Escalation Phase of this study.

Dose escalation follows a conventional 3+3 design: successive cohorts of 3 to 6 participants each will be evaluated in sequential escalating doses of single-agent IMGC936 (Table 1).

Each cycle is 21 days for Schedule A. IMGC936 is administered via IV infusion on Day 1 of Cycle 1 and every subsequent 21-day cycle thereafter at the assigned dose for each cohort in Schedule A. Infution duration will vary depending on dose and participant tolerability. Sentinel dosing will be used for the first 2 dose levels. The first administration of IMGC936 (Cycle 1) in participants at the first 2 dose levels of Schedule A dose escalation will be staggered by at least 48 hours.

Upon agreement between investigators and the sponsor, intermediate dose levels may be evaluated based on review of cumulative safety and PK data. For example, participants have been enrolled in intermediate dose cohorts at doses of 5mg/kg and 6 mg/kg.

**Table 1: IMGC936 Dose Levels: Dose Escalation** 

Cohort	IMGC936 Dose
Cohort 1	0.5 mg/kg
Cohort 2	1.0 mg/kg
Cohort 3	2.0 mg/kg
Cohort 4	4.0 mg/kg
Intermediate Dose	5.0 mg/kg
Intermediate Dose	6.0 mg/kg
Cohort 5	7.0 mg/kg
Cohort 6	10.0 mg/kg
Cohort 7	12.0 mg/kg

Dose escalation will follow standard 3 + 3 design until an MTD or MAD is established. To support the selection of the RP2D, upon agreement between investigators and the sponsor, any dose level not exceeding the MTD may be expanded to a maximum of 15 participants for further evaluation of safety, PK, antitumor activity, to facilitate selection of the RP2D. Intermediate dose levels, not exceeding the MTD, may also be explored.

Participants on Schedule A who are not able to complete the 21-day evaluation secondary to AEs considered unrelated to study drug or any other cause unrelated to study drug are considered unevaluable for safety and toxicity during the DLT evaluation period and may be replaced.

Participants may continue on study drug until disease progression, AE requiring discontinuation, withdrawal of consent, physician decision, or other discontinuation criteria are met.

If recommended by the Cohort Review Committee, in conjunction with the Sponsor, based on emerging safety, tolerability, PK, and preliminary antitumor activity of IMGC936, an alternate schedule (Schedule B) may be explored. Each cycle is 28 days in contrast to Schedule A, which is 21 days. Participants enrolled on Schedule B will receive study drug on Days 1, 8, and 15 of a 28-day cycle for the first 2 cycles. On all subsequent cycles (Cycle 3 and beyond), participants will receive study drug on Days 1 and 8 of a 28-day cycle (Table 3). To potentially reduce ocular or other safety events that may be driven by Cmax (maximum drug concentration after infusion), PK modeling suggests a fractionated weekly schedule would allow reduction in Cmax while maintaining AUC exposure. To reduce participant burden of an indefinite weekly schedule, starting from the third cycle, participants will only receive the study drug in the first 2 weeks in a 4-week cycle. The 3 + 3 dose escalation as described previously will apply to the alternate schedule. The recommended starting dose of 2 mg/kg/dose (Cycles 1 and 2) and 3 mg/kg/dose (Cycle 3 and beyond) for Schedule B in a 4-week cycle is less than the non-fractionated total dose of 7 mg/kg every 3 weeks, which was administered in Cohort 5 of Schedule A.

Table 3: IMGC936 Dose Levels: Dose Escalation (Schedule B)

Cohort	IMGC936 Dose on Days 1, 8, and 15 of Cycle 1 and Cycle 2	IMGC936 Dose on Days 1 and 8 of Cycle 3 and beyond	
Cohort B1	2 mg/kg/dose	3 mg/kg/dose	
Cohort B2	2.5 mg/kg/dose	3.5 mg/kg/dose	
Cohort B3	3.0 mg/kg/dose	3.5 mg/kg/dose	
Cohort B4	3.5 mg/kg/dose	4.0 mg/kg/dose	

Upon agreement between investigators and the sponsor, intermediate dose levels may be evaluated based on review of cumulative safety and PK data.

Participants on Schedule B who are not able to complete the 28-day evaluation secondary to AEs considered unrelated to study drug or any other cause unrelated to study drug are considered unevaluable for safety and toxicity during the DLT evaluation period and may be replaced.

#### 3.2.1. Dose escalation rule

Dose escalation will use a conventional 3 + 3 design. Participants who are not evaluable for safety for the full DLT evaluation period for reasons other than study drug-related toxicity may be replaced in the same dose-level cohort.

If 0 of the first 3 participants treated at a given dose level experience a DLT during the DLT evaluation period, the dose will be escalated, and 3 participants will be enrolled and treated at the next higher dose level.

If 1 of the first 3 participants treated at a given dose level experiences a DLT, then 3 additional participants will be enrolled at that dose level to further assess the safety of IMGC936.

- If  $\geq 1$  of these 3 additional participants (i.e.,  $\geq 2$  of the 6 participants) experience a DLT, it will be concluded that the MTD has been exceeded, and 3 participants will be enrolled and treated at the next lower dose level.
- If 0 of the 3 additional participants (i.e., ≤ 1 of the 6 participants) experience a DLT, then the dose will be escalated, and 3 participants will be enrolled at the next higher dose level.

If  $\geq 2$  of the first 3 participants treated at a given dose level, or  $\geq 2$  of 6 participants treated at a given dose level, experience a DLT, then it will be concluded that the MTD for IMGC936 has been exceeded at that dose level, and all subsequent participants will be treated at the next lower dose level.

For participants being treated at a dose level subsequently determined to exceed the MTD for a given cohort of the study, the dose of IMGC936 will be reduced to the next lower dose level as summarized in Table 1. Following these rules for dose escalation, the MTD/MAD will be the highest dose administered at which the incidence of DLT is < 33%.

Dose escalation to the next dose level is permitted only after the participants enrolled in the current dose cohort have completed the DLT evaluation period and the safety data have been

reviewed by the sponsor medical monitor and the investigators participating in the study. Evaluation of safety data from each cohort will include an assessment of the proportion of participants who receive planned doses, and the percentage of participants that require dose reductions or dose discontinuations for toxicity. All available data from participants both during and beyond the DLT evaluation period will be considered when making dose escalation decisions and in determination of the RP2D.

At the discretion of the sponsor, dose escalation may be stopped before an MTD is reached. In this case, the MAD may be chosen based on an assessment of PK, pharmacodynamics, biomarker, safety, and response data. An MTD does not have to be reached to expand a dose cohort if the available data demonstrate that a lower dose level may provide antitumor activity while minimizing potential risk.

At the discretion of the sponsor, any dose escalation cohort at a dose level not exceeding the MTD may be expanded to a maximum of 15 participants for further evaluation of safety, PK, and antitumor activity. Following determination of the RP2D, tumor-specific expansion cohorts may be opened in tumor types selected from those enrolled in dose escalation. The sponsor will provide a substantial amendment to applicable regulatory authorities for review and approval before opening these tumor-specific expansion cohorts.

## 3.3. Expansion Cohorts

The Dose Expansion Phase is designed to explore efficacy of IMGC936 at the RP2D as a single-agent in study participants with relapsed or refractory, unresectable locally advanced or metastatic solid tumors.

RP2D will be selected by the investigators and sponsor. Following determination of the RP2D, and at the sponsor's discretion, up to 7 expansion cohorts may be opened in tumor types selected from those enrolled in dose escalation (Table 4). Participants in Cohorts A through G can be enrolled in either in Dosing Schedule A or Schedule B upon sponsor's discretion.

**Table 4:** Expansion Cohorts

Cohort	IMGC936 Dose
Cohort A	Non-squamous NSCLC
Cohort B	TNBC
Cohort C	CRC
Cohort D	Gastroesophageal cancer
Cohort E	Pancreatic cancer
Cohort F	Any one above-mentioned tumor with an alternate dose and/or schedule
Cohort G	Any one above-mentioned tumor with an alternate dose and/or schedule

Participants may continue on study drug until disease progression, AE requiring discontinuation, withdrawal of consent, physician decision, or other discontinuation criteria are met.

A futility assessment will be conducted on the first 13 participants in each expansion cohort. If there are at least 2 responders out of 13 response-evaluable participants at the first stage, an additional 26 participants may be recruited to that cohort (full expansion) (for a total of 39 participants) to further evaluate safety, tolerability, PK, immunogenicity, biomarkers, antitumor activity, and survival of participants who received IMGC936.

The expansion cohorts may test more than 1 dose and/or schedule, not exceeding the MTD. Tumor types examined in Cohorts A to E may be further explored at a second dose and/or schedule in Cohorts F and G.

Tumor specimens for determination of ADAM9 expression via IHC staining will be collected from all participants and will be assayed at a central laboratory designated by the sponsor. ADAM9 testing results are not required for enrollment.

## 3.4. Study Population

Eligible patients will be  $\geq$  18 years of age and will have unresectable, relapsed or refractory, locally advanced or metastatic non-squamous NSCLC, TNBC, CRC, gastroesophageal cancer, or pancreatic cancer.

Patients who have consented to the study and who have received at least one dose of study drug will be considered enrolled. Patients who are issued a patient number but who do not successfully complete the screening process, and/or qualify but who do not receive a dose of study drug, will be considered screen failures. Patient numbers for patients who screen fail will not be reissued.

#### 3.4.1. Sample Size

The study plans to treat up to approximately 45 participants in dose escalation on Schedule A and up to 27 participants on Schedule B. The sample size is based on a 3 + 3 design with 7 planned dose cohorts of IMGC936. Additional participants may be enrolled if a dose cohort is expanded, participants are replaced, or intermediate dose levels are evaluated.

Each expansion cohort may be expanded independently following an optimal Simon's 2-stage design. If there are at least 2 responders out of 13 response-evaluable participants at the first stage, each may enroll an additional 26 participants to that cohort (a total of 39 participants).

#### 3.4.2. Assessment Schedule

See the protocol synopsis for study schedules of assessments.

#### 3.5. Interventions

IMGC936 is administered by IV infusion. The drug product is diluted in a solution of sterile Dextrose 5% in Water (D5W), United States Pharmacopeia (USP) in an IV bag for administration with an infusion pump.

IMGC936 is administered on Day 1 of each 21-day cycle. It is expected that Day 1 of subsequent cycles will be no more than 3 days after the previous cycle. IMGC936 is administered as an IV

infusion at the assigned dose for each cohort. Infusion duration will vary depending on dose and participant tolerability.

## 4. GENERAL ANALYTICAL CONSIDERATIONS

#### 4.1. Data Sources

Data including local laboratory data are recorded on eCRFs. The protocol provides additional details regarding data recording and handling.

#### 4.2. **Definition of Baseline**

Study Day 1 (ie, Cycle 1 Day 1) will be designated as the first day a patient receives study drug. The baseline value is defined as the last non-missing value on or before the date of first dose of study drug.

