- b Includes height (screening only) and weight. Weight may be obtained within 24 hours of Cycle 1 Day 1. Full physical examinations are performed at screening, Cycle 1 Day 1 (or within 24 hours before the first infusion), and EOTV. All other physical examinations are directed physical examinations based on symptoms, tumor location, and as clinically indicated. Participants in dose escalation cohorts will have weekly directed physical examination through treatment Cycle 3. Beginning on Cycle 4, physical examination is only required on Day 1 of each cycle. Participants in the dose expansion cohorts should have physical examination recorded on Day 1 of each treatment cycle.
- ^c ECOG performance status should be the primary performance measure for participant enrollment. If ECOG performance status is an inappropriate performance measurement for participant enrollment (eg, chronically nonambulatory), then Karnofsky performance status may be used. A description of the scale is in Appendix 8. ECOG assessment at C1D1 can be performed within 24 hours before the infusion.
- d On Day 1 of Cycle 1, 2 and 3, ECGs are recorded pre-infusion (within 30 minutes before) and EOI (within 30 minutes after EOI). During selected non-dosing visits (eg, screening, C1D8, and EOTV), ECGs will be recorded.
- ^e The Investigator to choose appropriate modality (eg, echocardiogram or MUGA) to assess LVEF.
- ophthalmic examinations are performed at screening by an ophthalmologist per Section 9.12. All participants will have a complete ophthalmological examination when ocular symptoms and signs develop, repeated per Table 7. Participants without ocular symptoms or signs should have an ophthalmic examination at the end of Cycle 2, followed with ophthalmic exams every 3 cycles/ 9 weeks (at the end of Cycle 5,8, etc.) in both dose escalation and expansion phases. Participants with Grade 2 or greater ocular AEs which have not resolved to Grade 1 or baseline must have an ophthalmic examination at EOTV. All other participants are recommended to have an ophthalmic examination at EOTV to document any subclinical findings.
- ^g Ocular symptom assessment at C1D1 can be performed within 24 hours before the infusion. For participants in dose escalation cohorts, ocular symptoms assessment should occur weekly during the first 3 cycles and subsequently Day 1 of each cycle. During the Dose Expansion Phase (at RP2D), if limited ocular

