toxicity is observed during escalation, ocular symptom assessment will occur on Day 1 of each cycle or more frequently if ocular symptoms and signs are observed. Phone-based ocular symptom assessments are acceptable if no clinic visit is scheduled.

- ^h Females of childbearing potential only. Serum pregnancy test is required for eligibility. Subsequent pregnancy tests may use serum or urine. Results must be reviewed before study drug infusion on Day 1 of Cycle 1 and all subsequent cycles. If screening test is performed within 72 hours of first infusion, repeat of the test on Day 1 may be deferred.
- During non-dosing visits (eg, screening and EOTV), vital signs will be taken at one timepoint. For Cycle 1 Day 1, vitals are measured pre-infusion (within 30 minutes before); 15 and 30 minutes after start of infusion (± 5 minutes); EOI (± 10 minutes); and 2, 4, and 6 hours after EOI (± 10 minutes). For Cycle 2 Day 1 and subsequent cycles, vitals are measured pre-infusion (within 30 minutes before), EOI (± 10 minutes), and 1 hour after EOI (± 10 minutes). Participants in dose escalation cohorts must have vital signs recorded on both dosing and non-dosing days through treatment Cycle 3. Beginning on Cycle 4, vital signs must be recorded on Day 1 of each treatment cycle. Participants in expansion cohorts must have vital signs recorded on Day 1 of each treatment cycle.
- ^j To be obtained pre-infusion. Day 1 laboratory samples can be obtained up to 3 days before infusion. Chemistry and hematology results must be reviewed before study drug administration. See Appendix 3 for assessments. Beginning on Cycle 4, laboratory samples only required on Day 1 of each cycle.
- ^k Tumor markers are obtained as indicated for each specific tumor type, eg, CEA for colorectal cancer and CA19-9 for pancreatic cancer. Repeat collection on Cycle 1 Day 1 if screening collection > 7 days prior.
- Tumor assessments are Q6W (\pm 7 days) while participant is on study drug, then Q12W (\pm 21 days). Assessments continue until discontinuation criteria are met. Tumor assessments are performed at EOTV except if prior assessment was \leq 30 days of EOTV and results are available for RECIST v1.1 assessment.
- ^m Tumor assessments will occur after participant has discontinued study drug Q12W (± 21 days) until evidence of PD, initiation of another anticancer therapy, withdrawal of consent, LTFU, death, or end of study, whichever occurs first.

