#### 7. SAFETY ANALYSES

The safety analyses will be performed on the Safety population. The assessments/events up to 30 days (inclusive) of the last dose of study drug or prior to the start of a new anti-cancer treatment, whichever occurs first, will be analyzed, unless otherwise stated. Baseline is defined as the last non-missing observed measurement prior to the first dose of study drug.

Unless otherwise stated, summaries of safety data will be presented for each dose level of IMGC936, combined RP2P dose (6mg/kg) as well as for overall of all patients in the Safety population.

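### SAP 4.2 and SAP 7 define baseline differently with no stated precedence, and the 4.2 rule, if programmed, would make post-infusion Day 1 ECGs and vital signs the baseline (minor)

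*SAP*

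**What the plan says.** The SAP defines baseline in two places.

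- SAP 4.2, the section named for the purpose, ties it to the calendar date: "The baseline value is defined as the last non-missing value on or before the date of first dose of study drug".
- The opening paragraph of SAP 7, which begins "The safety analyses will be performed on the Safety population", ties it to the dose: "Baseline is defined as the last non-missing observed measurement prior to the first dose of study drug".

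Neither sentence refers to the other, and the SAP gives no order of precedence. SAP 1.1 says that the SAP governs the analysis and that departures from it are to be documented.

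The protocol takes repeated readings on the first dosing day. For vital signs, the Appendix 1 footnote reads "For Cycle 1 Day 1, vitals are measured pre-infusion (within 30 minutes before); 15 and 30 minutes after start of infusion", then at end of infusion (EOI), "and 2, 4, and 6 hours after EOI". For ECGs it reads "On Day 1 of Cycle 1, 2 and 3, ECGs are recorded pre-infusion (within 30 minutes before) and EOI (within 30 minutes after EOI". Appendix 2 sets the same Cycle 1 Day 1 times for Schedule B.

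Two planned outputs depend on which of these readings is baseline. SAP 7.5 counts, by visit, participants whose QTcF rises more than 30 or more than 60 msec from baseline. SAP 7.4 tabulates the shift in vital-sign category from baseline to the last post-baseline visit.

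**The concern.** A rule based on the date treats everything recorded on the first dosing day as eligible for baseline, including readings taken after the drug has gone in. A rule based on the dose does not. For any measure repeated on Cycle 1 Day 1 the two rules choose different records.

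A programmer looking for the baseline rule would naturally open the section titled Definition of Baseline and could derive a single baseline flag from it for all data sets. QTcF changes and vital-sign shifts would then compare post-dose values with a post-dose reference. This is a first-in-human study, and Protocol 14.5.3 singles out QT prolongation as the main purpose of the ECG analysis, so the reference value should be free of drug.

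**Working it through.** The plan states no figure to reproduce. The check applies each rule to the Cycle 1 Day 1 schedule.

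**Step 1. Which record does each rule select?**

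| Measure | Cycle 1 Day 1 readings (Appendices 1 and 2) | SAP 4.2 | SAP 7 |
|---|---|---|---|
| Vital signs | pre-infusion; 15 and 30 min after start; EOI; 2, 4 and 6 h after EOI | 6 h after EOI | pre-infusion |
| ECG | pre-infusion; EOI | EOI | pre-infusion |
| Laboratory tests | pre-infusion only | pre-infusion | pre-infusion |

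**Step 2. Do the late readings fall on the dosing date?** Protocol 6.1 gives an infusion of about 2 to 3 hours. The last vital signs come up to 6 h 10 min after EOI and the ECG up to 30 min after EOI.

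- Vital signs, 2 h infusion: 24:00 − (2 h + 6 h 10 min) = 15:50. With 3 h: 24:00 − 9 h 10 min = 14:50.
- ECG, 2 h infusion: 24:00 − 2 h 30 min = 21:30. With 3 h: 24:00 − 3 h 30 min = 20:30.

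Any infusion started before those times leaves the reading on the dosing date. If the 6-hour set is missing, 4.2 falls back to the 4-hour set, which is still post-infusion.

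**Step 3. Does another section settle it?** No. SAP 4.4, on multiple assessments at one time point, gives no rule for choosing among same-day records. SAP 7.5 averages the triplicate within a time point but does not say which time point is baseline.

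**Step 4. What would 4.2 do to QTcF changes?** At Cycle 1 Day 1 EOI, the value minus itself is 0 for everyone. For later visits the following is an illustration with assumed inputs, none of them from the documents. Let s be the within-participant SD of a triplicate mean (8 to 12 msec), d the true shift at EOI, and f the share of d still present later. With normal errors:

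- pre-infusion baseline: P(change > 30) = 1 − Φ[(30 − f·d)/(s√2)]
- EOI baseline: P(change > 30) = 1 − Φ[(30 − (f·d − d))/(s√2)]

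For d = 20, f = 1, s = 8: s√2 = 11.3. The first is 1 − Φ(10/11.3) = 18.8%; the second is 1 − Φ(30/11.3) = 0.4%.

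| d (msec) | f | Pre-infusion baseline, s = 8 to 12 | EOI baseline, s = 8 to 12 |
|---|---|---|---|
| 10 | 1 | 3.9–11.9% | 0.4–3.9% |
| 20 | 1 | 18.8–27.8% | 0.4–3.9% |
| 30 | 1 | 50% | 0.4–3.9% |
| 20 | 0.5 | 3.9–11.9% | 0.02–0.9% |

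With the effect fully carried forward, the EOI baseline gives the same probability whatever the shift.

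**Step 5. What would 4.2 do to vital-sign shifts?** The direction depends on persistence. Take systolic pressure that is normal before infusion and high at 6 hours. If it is still high at the last visit, SAP 7 records normal to high and 4.2 records high to high, so the effect is lost. If it has returned to normal, SAP 7 records no shift and 4.2 records high to normal, a shift that did not occur relative to the untreated state.

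**The case against.** The strongest reply is that the SAP already handles this where it matters. Both exposed outputs lie inside SAP 7, whose opening paragraph requires a measurement before the first dose. A definition restated at the head of the safety chapter is most naturally read as governing that chapter, and it yields the pre-infusion reading. The harm therefore needs someone to program the general rule over the specific one. That argument stands, and it is why the point is conditional.

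Other parts of the reply also stand:

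- Laboratory values are unaffected, because Day 1 samples are drawn before infusion. The absolute QTcF categories (above 450, 480 and 500 msec) do not use baseline.
- The documents give no evidence of a QT effect. Protocol 2.5.1.2 reports no ECG findings in the monkey studies. The msec values above show a mechanism, not an expectation.
- The 6-hour vital signs are not certain to exist. Protocol 6.7.2 keeps participants under observation for 4 hours after the first infusion. This changes which post-infusion record 4.2 selects, not the fact that it is post-infusion.
- SAP 4.9 and 4.10 plan no hypothesis tests, and the response, PFS and DLT results do not depend on this.

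What does not stand is the idea that the placement of the SAP 7 sentence makes the 4.2 sentence harmless. Placement suggests precedence but does not state it, and the rule in the section titled for the purpose fails on this schedule.

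A reader might go further and infer that the planned safety analyses hide drug effects. The documents do not support that: under the rule written directly above those analyses, nothing is hidden. Nor is a bias toward no change established in general, because it requires the Day 1 effect to persist.

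**Conclusion.** The SAP contains two baseline definitions that disagree for Cycle 1 Day 1 ECGs and vital signs on both schedules, and it does not say which applies. The 4.2 rule is wrong for those measures: read literally it selects the EOI ECG and, for infusions started before about 14:50 to 15:50, the vital signs taken 6 hours after EOI. The SAP 7 rule is sound and is the more natural one to apply to the QTcF change categories and vital-sign shift tables.

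The consequence is conditional on 4.2 being programmed. If it were, the Cycle 1 Day 1 EOI change in QTcF would be zero by construction, persisting effects would be understated at later visits, and transient effects could appear as spurious shifts. The illustrative probabilities rest on the assumed SD, shift and persistence and should not be read as estimates for this drug. Severity is minor: an inconsistency in a basic derivation with limited reach, worth removing because doing so costs almost nothing.

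**What to change.** Restate SAP 4.2 so that baseline is the last non-missing value before the start, by date and time, of the first infusion. Where no clock time is collected, use the Day 1 record labelled pre-infusion, or the latest earlier value if that record is missing. Replace the baseline sentence in SAP 7 with a cross-reference to 4.2, so that only one definition remains.

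The cost is one rewritten sentence and one cross-reference, with no change to design, visits or data collection. Protocol 9.10 already has the actual ECG time recorded, and Protocol Appendix 4 already requires infusion start and end times on the eCRF. The documents do not say that a clock time is collected for vital signs, so the labelled pre-infusion record is the practical choice there.
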